When more than one measurable lesion is present at baseline, all lesions up to a maximum of five lesions total (and a maximum of two lesions per organ) representative of all involved organs should be identified as target lesions and will be recorded and measured at baseline. This means that, for instances in which patients have only one or two organ sites involved, a maximum of two lesions (one site) and four lesions (two sites), respectively, will be recorded. Other lesions (albeit measurable) in those organs will be considered non-target lesions.

Target lesions should be selected on the basis of their size (lesions with the longest diameter) and be representative of all involved organs, but in addition should lend themselves to reproducible repeated measurements. It may be the case that, on occasion, the largest lesion does not lend itself to reproducible measurement, in which circumstance the next largest lesion that can be measured reproducibly should be selected.

Lymph nodes merit special mention since they are normal anatomical structures that may be visible by imaging even if not involved by tumor. As noted above, pathological nodes that are defined as measurable and may be identified as target lesions must meet the criterion of a short axis of ≥ 15 mm by CT scan. Only the short axis of these nodes will contribute to the baseline sum. The short axis of the node is the diameter normally used by radiologists to judge if a node is involved by solid tumor. Lymph node size is normally reported as two dimensions in the plane in which the image is obtained (for CT, this is almost always the axial plane; for MRI, the plane of acquisition may be axial, sagittal, or coronal). The smaller of these measures is the short axis. For example, an abdominal node that is reported as being 20 mm \times 30 mm has a short axis of 20 mm and qualifies as a malignant, measurable node. In this example, 20 mm should be recorded as the node measurement. All other pathological nodes (those with short axis ≥ 10 mm but < 15 mm) should be considered non-target lesions. Nodes that have a short axis of < 10 mm are considered non-pathological and should not be recorded or followed.

All lesions (or sites of disease) not selected as target lesions (measurable or non-measurable), including pathological lymph nodes, should be identified as non-target

Appendix 4

Response Evaluation Criteria in Solid Tumors: Modified-Immune Criteria (Excerpt from Original Publication) (cont.)

lesions and should also be recorded at baseline. Measurements are not required. It is possible to record multiple non-target lesions involving the same organ as a single item on the Case Report Form (CRF) (e.g., "multiple enlarged pelvic lymph nodes" or "multiple liver metastases").

NEW LESIONS

New lesions identified after baseline will be evaluated for measurability with use of the same criteria applied to prospective target lesions at baseline per RECIST (e.g., non-lymph node lesions must be ≥ 10 mm on the longest diameter; new lymph nodes must be ≥ 15 mm on the short axis [see note below]). All new lesions (measurable or non-measurable) must be assessed and recorded at the time of identification and at all subsequent tumor assessment timepoints.

Up to a maximum of five measurable new lesions total (and a maximum of two lesions per organ) can be included in the calculation of tumor burden that is performed as part of the tumor response evaluation. New lesion types that would not qualify as target lesions per RECIST cannot be included in the calculation of tumor burden and thus will not affect overall tumor response evaluation. New lesions that are not measurable at first appearance but meet measurability criteria at a subsequent timepoint can be included in the tumor response evaluation from that point on, if the maximum number of measurable new lesions has not been reached.

Note regarding new lymph node lesions: If at first appearance the short axis of a lymph node lesion is ≥ 15 mm, it will be considered a measurable new lesion. If at first appearance the short axis of a lymph node lesion is ≥ 10 mm and < 15 mm, the lymph node will not be considered measurable but will still be considered a new lesion and should be identified as a non-measurable new lesion. If at first appearance the short axis of a lymph node is < 10 mm, the lymph node should not be considered pathological and should not be considered a new lesion. A lymph node can subsequently become measurable, when the short axis is ≥ 15 mm.

CALCULATION OF SUM OF DIAMETERS

A sum of the diameters (longest diameter for non-lymph node lesions, short axis for lymph node lesions) will be calculated for all target lesions at baseline as a measure of tumor burden. At each subsequent tumor assessment, a sum of the diameters (longest diameter for non-lymph node lesions, short axis for lymph node lesions) will be calculated for all target lesions plus measurable new lesions (up to five new lesions, with a maximum of two new lesions per organ) that have emerged after baseline. Hence,

Appendix 4

Response Evaluation Criteria in Solid Tumors: Modified-Immune Criteria (Excerpt from Original Publication) (cont.)

each net percentage change in tumor burden per assessment accounts for the size and growth kinetics of both old lesions and new lesions as they appear.

Measuring Lymph Nodes

If at first appearance the short axis of a new lymph node lesion is ≥ 15 mm, it will be considered a measurable new lesion and may be included in the sum of the diameters. If the new lymph node lesion is included in the sum of diameters, it will continue to be measured and included in the sum of diameters at subsequent timepoints, even if the short axis decreases to < 15 mm (or even < 10 mm). However, if it subsequently decreases to < 10 mm and all other lesions are no longer detectable or have also decreased to a short axis of < 10 mm (if lymph nodes), a response assessment of complete response may be assigned.

Lymph nodes should always have the actual short axis measurement recorded (measured in the same anatomical plane as the baseline examination), even if the node regresses to < 10 mm during the study. Thus, when lymph nodes are included in the sum of diameters, the sum may not be zero even if complete response criteria are met, since a normal lymph node is defined as having a short axis of < 10 mm.

Measuring Lesions That Become Too Small to Measure

During the study, all target lesions and up to five measurable new lesions (lymph node and non-lymph node) should have their actual measurements recorded at each subsequent evaluation, even when very small (e.g., 2 mm). However, sometimes lesions or lymph nodes become so faint on CT scan that the radiologist may not feel comfortable assigning an exact measurement and may report them as being too small to measure. When this occurs, it is important that a value be recorded on the CRF, as follows:

- If it is the opinion of the radiologist that the lesion has likely disappeared, the measurement should be recorded as 0 mm.
- If the lesion is believed to be present and is faintly seen but too small to measure, a default value of 5 mm should be assigned and "too small to measure" should be ticked. (Note: It is less likely that this rule will be used for lymph nodes since they usually have a definable size when normal and are frequently surrounded by fat such as in the retroperitoneum; however, if a lymph node is believed to be present and is faintly seen but too small to measure, a default value of 5 mm should be assigned in this circumstance as well and "too small to measure" should also be ticked).

Appendix 4 Response Evaluation Criteria in Solid Tumors: Modified-Immune Criteria (Excerpt from Original Publication) (cont.)

To reiterate, however, if the radiologist is able to provide an actual measurement, that should be recorded, even if it is <5 mm, and in that case "too small to measure" should not be ticked.

Measuring Lesions That Split or Coalesce on Treatment

When non-lymph node lesions fragment, the longest diameters of the fragmented portions should be added together to calculate the sum of diameters. Similarly, as lesions coalesce, a plane between them may be maintained that would aid in obtaining maximal diameter measurements of each individual lesion. If the lesions have truly coalesced such that they are no longer separable, the vector of the longest diameter in this instance should be the maximum longest diameter for the coalesced lesion.

EVALUATION OF NON-TARGET LESIONS AND NON-MEASURABLE NEW LESIONS

Measurements are not required for non-target lesions or non-measurable new lesions. Non-target lesions should be noted at baseline, and non-measurable new lesions should be noted at the time of identification. At subsequent evaluations, non-target lesions and non-measurable new lesions will be categorized as "present" or "absent."

After baseline, changes in non-target lesions or non-measurable new lesions (or measurable new lesions in excess of five total or two per organ) will contribute only in the assessment of complete response (i.e., a complete response is attained only with the complete disappearance of all tumor lesions, including non-target lesions and non-measurable new lesions) and will not be used to assess progressive disease.

RESPONSE CRITERIA

Definitions of the criteria used to determine objective tumor response are provided below:

- Complete response (CR): Disappearance of all lesions
 Any pathological lymph nodes must have reduction in short axis to < 10 mm.
- Partial response (PR): At least a 30% decrease in the sum of diameters of all target lesions plus measurable new lesions (up to a maximum of five total or two per organ), taking as reference the baseline sum of diameters, in the absence of CR

Appendix 4

Response Evaluation Criteria in Solid Tumors: Modified-Immune Criteria (Excerpt from Original Publication) (cont.)

- Progressive disease (PD): At least a 20% increase in the sum of diameters of all target lesions plus measurable new lesions (up to a maximum of five total or two per organ), taking as reference the smallest sum of diameters on study (including baseline)

In addition to the relative increase of 20%, the sum of diameters must also demonstrate an absolute increase of ≥ 5 mm.

New lesions alone do not qualify as progressive disease. However, their contribution to total tumor burden is factored into the sum of the diameters, which is used to determine the overall immune-modified RECIST tumor response.

- Stable disease (SD): Neither sufficient shrinkage to qualify for CR or PR nor sufficient increase to qualify for PD

CRITERIA FOR OVERALL RESPONSE AT A SINGLE TIMEPOINT

Table 2 provides a summary of the overall response status calculation at each response assessment timepoint for patients who have measurable disease at baseline.

Table 2 Criteria for Overall Response at a Single Timepoint: Patients with Target Lesions (with or without Non-Target Lesions)

Target Lesions and Measurable New Lesions ^a	Non-Target Lesions and Non-Measurable New Lesions ^b	Overall Response
CR	Absent	CR
CR	Present or not all evaluated	PR
PR	Any	PR
SD	Any	SD
Not all evaluated	Any	NE
PD	Any	PD

CR=complete response; NE=not evaluable; PD=progressive disease; PR=partial response; SD=stable disease.

^a Up to a maximum of five measurable new lesions total (and a maximum of two lesions per organ) can be included in the calculation of tumor burden, in addition to the target lesions identified at baseline.

^b Also includes measurable new lesions in excess of five total or two per organ.

Appendix 4 Response Evaluation Criteria in Solid Tumors: Modified-Immune Criteria (Excerpt from Original Publication) (cont.)

MISSING ASSESSMENTS AND NOT-EVALUABLE DESIGNATION

When no imaging/measurement is done at all at a particular timepoint, the patient is not evaluable at that timepoint. If measurements are made on only a subset of target or measurable new lesions at a timepoint, usually the case is also considered not evaluable at that timepoint, unless a convincing argument can be made that the contribution of the individual missing lesions would not change the assigned timepoint response. This would be most likely to happen in the case of PD. For example, if a patient had a baseline sum of 50 mm with three measured lesions and during the study only two lesions were assessed, but those gave a sum of 80 mm, the patient will have achieved PD status, regardless of the contribution of the missing lesion.

SPECIAL NOTES ON RESPONSE ASSESSMENT

Patients with a global deterioration in health status requiring discontinuation of treatment without objective evidence of disease progression at that time should be reported as "symptomatic deterioration." Every effort should be made to document objective progression even after discontinuation of treatment. Symptomatic deterioration is not a descriptor of an objective response; it is a reason for stopping study therapy. The objective response status of such patients is to be determined by evaluation of target and non-target lesions, as well as new lesions, as shown in [Table 1](#).

REFERENCES

Appendix 5

Eastern Cooperative Oncology Group Performance Status Scale

Grade	Description
0	Fully active, able to carry on all predisease performance without restriction
1	Restricted in physically strenuous activity but ambulatory and able to carry out work of a light or sedentary nature (e.g., light housework or office work)
2	Ambulatory and capable of all self-care but unable to carry out any work activities; up and about > 50% of waking hours
3	Capable of only limited self-care, confined to a bed or chair > 50% of waking hours
4	Completely disabled; cannot carry on any self-care; totally confined to bed or chair
5	Dead

Appendix 6

Preexisting Autoimmune Diseases and Immune Deficiencies

Patients should be carefully questioned regarding their history of acquired or congenital immune deficiencies or autoimmune disease. Patients with any history of immune deficiencies or autoimmune disease listed in the table below are excluded from participating in the study. Possible exceptions to this exclusion could be patients with a medical history of such entities as atopic disease or childhood arthralgias for whom the clinical suspicion of autoimmune disease is low. Patients with a history of autoimmune-related hypothyroidism on a stable dose of thyroid-replacement hormone may be eligible for this study. In addition, transient autoimmune manifestations of an acute infectious disease that resolved upon treatment of the infectious agent are not excluded (e.g., acute Lyme arthritis). Contact the Medical Monitor regarding any uncertainty about autoimmune exclusions.

Autoimmune Diseases and Immune Deficiencies


 • Acute disseminated encephalomyelitis • Addison disease • Ankylosing spondylitis • Antiphospholipid antibody syndrome • Aplastic anemia • Autoimmune hemolytic anemia • Autoimmune hepatitis • Autoimmune hypoparathyroidism • Autoimmune hypophysitis • Autoimmune myocarditis • Autoimmune oophoritis • Autoimmune orchitis • Autoimmune thrombocytopenic purpura • Behçet disease • Bullous pemphigoid • Chronic fatigue syndrome • Chronic inflammatory demyelinating polyneuropathy • Churg-Strauss syndrome • Crohn disease 	
 • Dermatomyositis • Diabetes mellitus type 1 • Dysautonomia • Epidermolysis bullosa acquisita • Gestational pemphigoid • Giant cell arteritis • Goodpasture syndrome • Graves disease • Guillain-Barré syndrome • Hashimoto disease • IgA nephropathy • Inflammatory bowel disease • Interstitial cystitis • Kawasaki disease • Lambert-Eaton myasthenia syndrome • Lupus erythematosus • Lyme disease, chronic • Meniere syndrome • Mooren ulcer • Morphea • Multiple sclerosis • Myasthenia gravis 	
 • Neuromyotonia • Opsoclonus myoclonus syndrome • Optic neuritis • Ord thyroiditis • Pemphigus • Pernicious anemia • Polyarteritis nodosa • Polyarthrits • Polyglandular autoimmune syndrome • Primary biliary cirrhosis • Psoriasis • Reiter syndrome • Rheumatoid arthritis • Sarcoidosis • Scleroderma • Sjögren syndrome • Stiff-Person syndrome • Takayasu arteritis • Ulcerative colitis • Vitiligo • Vogt-Koyanagi-Harada disease • Wegener granulomatosis
--	---	--

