aPD-1 = anti-programmed cell death 1; ECOG = Eastern Cooperative Oncology Group; PD = progressive disease; PS = performance score; RECIST = Response Evaluation Criteria in Solid Tumors.

Figure 5 Treatment and Biopsy Schedule (Cohort A)

[figure not shown]
D = day; IV = intravenous; PO = by mouth.

Figure 6 Treatment and Biopsy Schedule (Cohort B)

D= day; IV= intravenous; PO= by mouth.

Figure 7 Treatment and Biopsy Schedule (Cohort C)

D= day; IV= intravenous.

After signing informed consent, eligible patients will undergo screening procedures that include testing for the *BRAF*^{V600} mutation; laboratory tests; 12-lead ECGs; left ventricular function evaluation (LVEF; echocardiogram [ECHO] or multiple-gated acquisition [MUGA] scan); contrast-enhanced brain computed tomography (CT) scan or magnetic resonance imaging (MRI); contrast-enhanced CT or MRI scan of the chest, abdomen, and pelvis; and ophthalmologic (for Cohorts A and B) and dermatologic assessments.

All patients will be closely monitored for safety and tolerability throughout the study. The National Cancer Institute Common Terminology Criteria for Adverse Events, Version 4.0 (NCI CTCAE v4.0) will be used to characterize the toxicity profile of the study treatments for all patients. The protocol includes a detailed risk management plan for monitoring and managing molecule-specific and potential combination toxicities (see Section 5).

For all cohorts, tumor response will be evaluated by the investigator according to RECIST v1.1 (see Appendix 3); immune-modified RECIST v1.1 (see Appendix 4) will also be assessed by the investigator. For Cohort C, tumor response will also be determined by the independent review committee (IRC) according to RECIST v1.1. All measurable and non-measurable lesions will be documented at screening. Response will be assessed at 8-week intervals until investigator-determined disease progression (according to RECIST v1.1), death, or initiation of subsequent anti-cancer therapy, whichever occurs first. Patients who experience disease progression must have scans repeated 4 weeks after initial documentation of progression to confirm disease progression. Tumor assessments are to continue according to schedule in patients who discontinue treatment for reasons other than confirmed disease progression, unless subsequent anti-cancer therapy is initiated.

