Response Evaluation Criteria in Solid Tumors: Modified-Immune Criteria (Excerpt from Original Publication)

Conventional response criteria may not be adequate to characterize the anti-tumor activity of immunotherapeutic agents like atezolizumab, which can produce delayed responses that may be preceded by initial apparent radiographic progression, including the appearance of new lesions. Therefore, immune-modified response criteria have been developed to incorporate new lesions into the assessment of total tumor burden and allow radiographic progression to be confirmed at a subsequent assessment. Immune-modified Response Evaluation Criteria in Solid Tumors (RECIST), as described within this appendix, were adapted from RECIST, Version 1.1 (v1.1) (Eisenhauer et al. 2009), in the same manner that immune-related response criteria were adapted from WHO criteria (Wolchok et al. 2009) and RECIST v1.0 (Nishino et al. 2014). When not otherwise specified, RECIST v1.1 conventions will apply. Differences between immune-modified RECIST and RECIST v1.1 are summarized in [Table 1](#).

Table 1 Comparison of RECIST v1.1 and Immune-Modified RECIST

	RECIST v1.1	Immune-Modified RECIST
Measurable new lesions	Always represent progression	Incorporated into the total tumor burden ^a and followed
Non-measurable new lesions	Always represent progression	Do not represent progression, but preclude CR
Non-target lesions	Contribute to defining CR, PR, SD, and PD	Contribute to defining CR only
CR	Disappearance of all lesions	Disappearance of all lesions
PR	≥30% decrease in sum of diameters of target lesions, in the absence of CR, new lesions, and unequivocal progression in non-target lesions	≥30% decrease in tumor burden, ^a in the absence of CR
PD	≥20% increase in sum of diameters of target lesions, unequivocal progression in non-target lesions, and/or appearance of new lesions	≥20% increase in tumor burden ^a
SD	Neither sufficient shrinkage to qualify for CR or PR nor sufficient increase to qualify for PD	Neither sufficient shrinkage to qualify for CR or PR nor sufficient increase to qualify for PD

CR=complete response; PD=progressive disease; PR=partial response; RECIST=Response Evaluation Criteria in Solid Tumors; SD=stable disease.

^a Tumor burden is the sum of diameters of target lesions and measurable new lesions.

Appendix 4

Response Evaluation Criteria in Solid Tumors: Modified-Immune Criteria (Excerpt from Original Publication) (cont.)

TUMOR MEASURABILITY

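### Appendix 4 announces confirmation of immune-modified progression but no rule applies it, so a tumour-burden flare that later reverses still ends immune-modified PFS

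*Combined protocol and SAP*

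**What the plan says.** Appendix 4 introduces immune-modified RECIST as a way to bring new lesions into the tumour burden and to "allow radiographic progression to be confirmed at a subsequent assessment". The operative text that follows is:

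- **PD.** "At least a 20% increase in the sum of diameters of all target lesions plus measurable new lesions", measured against the smallest sum on study, with an absolute rise of at least 5 mm.
- **New and non-target lesions.** "New lesions alone do not qualify as progressive disease". The Table 1 entry for non-measurable new lesions is "Do not represent progression, but preclude CR". Changes in non-target lesions "will not be used to assess progressive disease".
- **PR.** A fall of at least 30%, "taking as reference the baseline sum of diameters, in the absence of CR".
- **Default.** "When not otherwise specified, RECIST v1.1 conventions will apply".

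Section 6.4.3 analyses immune-modified ORR, DOR and PFS by the methods already given for the RECIST v1.1 endpoints. In Section 6.4.2, PFS runs to the first progression or death. In Section 6.4.1, a response is two consecutive CR or PR assessments at least 4 weeks apart. Section 3.1 adds: "Patients who experience disease progression must have scans repeated 4 weeks after initial documentation of progression to confirm disease progression".

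**The concern.** Sections 3.1.2 and 3.3.4 describe pseudoprogression as an early increase in tumour burden from immune-cell infiltration. The immune-modified endpoints exist to look past it. Yet the immune-modified PD criterion is itself a rise in tumour burden, and nothing in Appendix 4 makes that rise conditional on a later scan. For this form of pseudoprogression the stated purpose and the written rule disagree.

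At stake is whether immune-modified PFS can show what it was added to show. If the gap is left open, someone must decide at analysis whether the introductory sentence of Appendix 4 or the PD definition governs. The study is open-label and these endpoints are investigator-assessed, so that decision is better made before the data are seen.

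**Working it through.** The plan states no figure on this point to reproduce. The check applies the written definitions to illustrative lesion series.

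**Rules (Appendix 4).** Let S be the sum of target plus measurable new lesions, S0 the baseline sum, and N the smallest earlier sum including baseline.
- PD: S ≥ 1.2 × N and S − N ≥ 5 mm.
- PR: S ≤ 0.7 × S0.
- Otherwise SD.

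**Series (S0 = 50 mm).** Weeks 8, 16 and 24 are scheduled scans; Week 12 is the repeat scan 4 weeks after Week 8. Percentages are changes from baseline. At Weeks 8 and 12 baseline is also the nadir.

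| Series | Week 8 | Week 12 | Week 16 | Week 24 |
|---|---|---|---|---|
| 1. Target growth only | 62 (+24%, +12 mm): PD | 48 (−4%): SD | 34 (−32%): PR | 32 (−36%): PR |
| 2. Smaller new lesion | 45+10 = 55 (+10%): SD | 38+10 = 48 (−4%): SD | 25+8 = 33 (−34%): PR | 22+5 = 27 (−46%): PR |
| 3. Larger new lesion | 50+12 = 62 (+24%, +12 mm): PD | 45+10 = 55 (+10%): SD | 26+6 = 32 (−36%): PR | 25+5 = 30 (−40%): PR |

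The later scans can exist. Section 4.4.5 continues imaging until progression is confirmed, and the tumour-assessment footnote in Appendix 1 continues it to loss of clinical benefit in patients treated beyond progression.

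**RECIST v1.1 PFS.** All three series are events at Week 8: target growth in series 1, a new lesion in series 2 and 3.

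**Immune-modified PFS as written.** Series 2 has no event through Week 24, so the new-lesion rule works. Series 1 and 3 are events at Week 8.

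**Immune-modified PFS with confirmation.** At Week 12, series 1 is at −4% and series 3 at +10%. Neither meets PD, so neither has an event through Week 24.

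**Immune-modified ORR as written.** All three have PR at Weeks 16 and 24, which are 8 weeks apart. PR is measured from baseline, and Section 6.4.1 does not require the response to precede any progression. All three are responders with or without confirmation.

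**Immune-modified DOR.** The clock starts at the first response, Week 16, so a Week 8 flare falls outside the interval. Only a burden rise that occurs after a response and then reverses would end DOR.

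As written, series 1 and 3 are therefore PFS events at Week 8 and responders from Week 16, and no text reconciles the two.

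**Does the RECIST v1.1 default supply confirmation?** No. PD in Appendix 3 needs none. Its provision for dating progression back after a later scan covers equivocal findings only.

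**Size, by assumption.** The documents give no rate of reversed burden flares. If 3% to 10% of all planned patients had one, 152 × 0.03 = 4.6 and 152 × 0.10 = 15.2, or about 5 to 15 patients whose immune-modified PFS time would change.

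**The case against.** The strongest reply is that Appendix 4 already removes most of the problem. RECIST v1.1 reaches PD by target growth, non-target progression or a new lesion. Under the immune-modified criteria the second route is closed, and the third counts only through a rise of at least 20% and 5 mm in total burden. That is correct, and it limits the point to burden growth. It does not dispose of it, because burden growth is how the protocol itself describes pseudoprogression.

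Two stronger readings are tempting, and the documents do not support them. A reader might infer that immune-modified ORR also loses late responders, perhaps by carrying over a RECIST v1.1 habit of stopping at PD. Neither Section 6.4.1 nor Appendix 4 says so, and the best-response table in Appendix 3 has no row that starts with PD. A reader might also infer that the 4-week repeat scan serves no purpose. It has a stated role in continuing treatment and imaging (Sections 3.1, 3.3.4 and 4.4.5), and nothing bars its measurements from feeding the response assessment. What is missing is a rule that lets it overturn a PD for PFS or DOR.

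It is also fair to object that a simple requirement for confirmation could do harm. Starting new anti-cancer therapy stops tumour assessments under Section 3.1. Patients who do so, or who withdraw before the repeat scan, would become non-events, which would censor likely progressors and inflate PFS. This objection stands and shapes the fix.

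**Conclusion.** The point holds for immune-modified PFS, and for immune-modified DOR only when a reversed flare follows a response. Appendix 4 states a purpose that its PD rule, read with Sections 6.4.2 and 6.4.3, does not carry out. ORR needs only one clarifying sentence, because the text already counts a response after a flare.

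The consequence is small. The affected endpoints are exploratory, Section 6.1 plans no formal testing, and the co-primary and secondary endpoints do not change. The conclusion about the definitions rests on the text alone. The 5 to 15 patients rest on an assumed rate across all three cohorts and should not be read as an estimate. This is a cheap improvement, not a defect that threatens the study's conclusions.

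**What to change.** Add to Appendix 4, and refer to it in Section 6.4.3:

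1. Immune-modified PD is a PFS or DOR event, dated at the first scan that meets PD, unless a repeat scan at least 4 weeks later no longer meets PD.
2. PD with no later evaluable scan, for any reason (death, deterioration, new anti-cancer therapy, withdrawal or loss to follow-up), remains an event at the first PD date.
3. A response after an unconfirmed PD counts towards immune-modified ORR.

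This changes the analysis only; no treatment rule is touched. The cost is a few sentences, a little extra programming, and an immune-modified PFS that is less directly comparable with RECIST v1.1 PFS. No new scans are needed. The mandated repeat scan follows RECIST v1.1 progression. Where immune-modified PD arises later than that, the next available scan at least 4 weeks on can serve, and item 2 applies if there is none.
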